5.5.3 Safety parameters and analyses

The assessment of safety will be based mainly on the frequency of adverse events (AEs), on the number of patients with laboratory values that fall outside of reference ranges and the number of patients with clinically notable ECG data. Other safety data (e.g vital signs, special tests) will be considered as appropriate.

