#### 7.5.2.2 Changes in QT interval

If, at any visit, a QTcF > 480 msec is seen in patients receiving pasireotide LAR, the following actions will be taken:

- A visit to a cardiologist must be scheduled as soon as possible, but within no more than 7 days of the initial abnormal ECG, and the cardiologist must re-evaluate the ECG (this can be done by the central cardiologist, if the study has one).
  - o If a QTcF > 480 msec is NOT confirmed, no action will be taken.
  - o If a QTcF > 480 msec is confirmed, a cardiologist must perform a thorough examination (such as review of baseline ECG, concurrent medication, and performance of a cardiovascular examination (including, at least, one cardiac auscultation)) in order to evaluate the patient for cardiovascular risk factors.
  - o If, based on the cardiologist's evaluation, the investigator considers that there is an acute cardiovascular safety risk and that the patient should not continue to receive the study drug, or the patient meets any discontinuation criteria (section 6.4.5.1), he/she must be immediately discontinued.

- If, after the cardiologist's examination, the investigator considers that there is no acute cardiovascular safety risk and that the patient may continue to receive the study drug, then, the following actions must be taken:
- Scenario A (Figure 7-1): If the initial ECG was performed before the pasireotide LAR injection:

A (24-hour) Holter ECG must be recorded as soon as possible, but within no more than 7 days of the initial abnormal ECG. The cardiologist evaluates the Holter ECG and provides the investigator with recommendations. The investigator analyzes the results and the cardiologist's recommendations. If a patient meets the discontinuation criteria (section 6.4.5.1), he/she will be immediately discontinued.

[figure not shown]
If a patient does not meet the discontinuation criteria, the next pasireotide LAR dose may be administered. A second Holter ECG must be recorded on the day of the next pasireotide LAR injection, and it must be started 30 min before the study drug injection. ECG, cardiac examination, and Holter ECG results, as well as the cardiologist's recommendation, must be evaluated by the investigator in order to determine whether the patient may or may not continue in the study (discontinuation criteria to be followed, Section 6.4.4 and Section 6.4.5).

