# 7.5.8 Electrocardiogram (ECG)

All ECGs will be locally performed. An ECG will be performed in the Screening Period or Visit 1 (to evaluate eligibility) and then on all visits before injection of the study drug in the Main Phase, except for Visits 3 and 6, on which they will be performed independently of drug administration. In the Extension Phase, ECGs will be performed on Weeks 36, 48, 60, 72, 84, and 96.

It is recommended that paper speed be programmed to 25 mm/s, and sensitivity to 10 mm/mV (calibration). The operator must sign and date all tracings performed. The abnormalities seen must be recorded in the ECG eCRF.

If a clinically significant abnormality is detected, the ECG will be repeated, at the Investigator's discretion, until the abnormality is resolved. More frequent ECGs may be performed at the Investigator's discretion, if clinically indicated. Any abnormalities must be recorded in the unscheduled evaluation pages of the eCRF.

Data safety records must include the following:

- Any abnormal ECG findings (refer to Section 7.5.2.2)
- Abnormal vital signs
- All arrhythmias, including: Torsades de Pointes, ventricular tachycardia, ventricular fibrillation, and ventricular flutter
- Syncope, near-syncope, and fainting
- Seizures or loss of central function (sudden incontinence, dizziness, visual disorders)
- Sudden death

The study number must be recorded as [CSOM230D2401] at each tracing and must be kept in the source-documents.

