#### 10.5.3 Safety analyses and parameters

The safety evaluation will be based mainly on frequency of adverse events (AEs), number of patients with laboratory values outside the reference ranges, and number of patients with clinically significant changes in ECGs. Other safety data (for example, vital signs and special tests) will be considered when appropriate.

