Standard Deviation			
Minimum			
Maximum			
Free T4 (ng/dL) at V1			
N			
Mean			
Median			
Standard Deviation			
Minimum			
Maximum			

Table 32 – Vital signs – Safety population

	Total (n=xx)									
	V1	V2	V3	V4	V5	V6	V7	V8	V9	V10
Systolic blood pressure (mmHg) N Mean Median Standard Deviation Minimum										
Maximum										
Diastolic blood pressure (mmHg) N Mean Median Standard Deviation Minimum Maximum Heart rate (bpm) N Mean Median										
Standard Deviation Minimum Maximum										
Temperature (ºC) N Mean Median Standard Deviation Minimum Maximum										

Table 33 – Physical examination – Safety population

	Total (n=xx)									
	V1	V2	V3	V4	V5	V6	V7	V8	V9	V10
Height (cm)										
N		-	-	-	-	-	-	-	-	-
Mean		-	-	-	-	-	-	-	-	-
Median		-	-	-	-	-	-	-	-	-
Standard Deviation		-	-	-	-	-	-	-	-	-
Minimum		-	-	-	-	-	-	-	-	-
Maximum		-	-	-	-	-	-	-	-	-
Weight (kg) N										
Mean										
Median										
Standard Deviation										
Minimum										
Maximum										
Findings, n (%)										
Normal										
Abnormal										
Skin and nails										
Eves										
Nose and sinuses										
Ears										
Mouth and pharynges										
Head and neck										
Thorax and lungs										
Breast										
Abdomen										
Lymphatic										
Extremities										
Vascular										
Neurological										

Table 34 – Eastern cooperative oncology group performance status – Safety population

	Total (n=xx)									
	V1	V2	V3	V4	V5	V6	V7	V8	V9	V10
ECOG result, n (%)										
0										
1										
2										
3										
4										
5										
Total										

ECOG: Eastern Cooperative Oncology Group.

Table 35 – Electrocardiogram – Safety population

	Total (n=xx)									
	V1	V2	V3	V4	V5	V6	V7	V8	V9	V10
QTcF (msec) N Mean Median Standard Deviation Minimum Maximum										
Result, n (%) Normal Abnormal without clinical significance Abnormal with clinical significance Total Consultation with cardiologist to confirm abnormal ECG?, n (%) Yes										
No Total										
If yes, cardiologist confirm QTcF interval >480msec, n (%) Yes No Total										
Patient discontinued after thorough cardiological examination. n (%) Yes No Total										

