	Total							
	(n=xx)							
-	V13	V16	V19	V22	V25	V28	V29	

Systolic blood pressure (mmHg)

Mean

Median

Standard Deviation

Minimum

Maximum

Diastolic blood pressure (mmHg)

Mean

Median

Standard Deviation

Minimum

Maximum

Heart rate (bpm)

Mean

Median

Standard Deviation

Minimum

Maximum

Temperature (ºC)

Ν

Mean Median

Standard Deviation

Minimum

Maximum

Table B 25 – Physical examination – Safety population

	Total (n=xx)						
	V13	V16	V19	V22	V25	V28	V29
Weight (kg)							
N							
Mean							
Median							
Standard Deviation							
Minimum							
Maximum							
Findings, n (%)							
Normal							
Abnormal							
Skin and nails							
Eves							
Nose and sinuses							
Ears							
Mouth and pharynges							
Head and neck Thorax and lungs							
Breast							
Abdomen							
Lymphatic							
Extremities							
Vascular							
Neurological							

Table B 26 – Eastern cooperative oncology group performance status – Safety population

	Total (n=xx)							
	V13	V16	V19	V22	V25	V28	V29	
ECOG result, n (%)								
0								
1								
2								
3								
4								
5								
Total								

ECOG: Eastern Cooperative Oncology Group.

Table B 27 – Electrocardiogram – Safety population

	Total					
	(n=xx) V13	V16	V19	V22	V25	V28
QTcF (msec)						
N N						
Mean						
Median						
Standard Deviation						
Minimum						
Maximum						
Result, n (%)						
Normal						
Abnormal without clinical						
Abnormal with clinical						
Total						
Consultation with cardiologist to						
confirm abnormal ECG?, n (%)						
Yes						
No						
Total						
If yes, cardiologist confirm QTcF						
interval >480msec, n (%)						
Yes						
No						
Total						
Patient discontinued after						
thorough cardiological						
examination, n (%)						
Yes						
No						
Total

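### The SAP never defines a clinically notable ECG, and neither ECG table counts the patients affected at any visit

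*SAP*

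**What the plan says.** SAP 5.5.3 names three main safety measures: adverse event frequency, patients with laboratory values outside the reference range, and "the number of patients with clinically notable ECG data". Protocol 10.5.3 words the third as the "number of patients with clinically significant changes in ECGs". Neither section gives a threshold or rule for what counts.

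Table 35 (columns V1 to V10) and Table B 27 (columns V13, V16, V19, V22, V25 and V28) share the same rows:

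- QTcF descriptive statistics, including minimum and maximum
- the overall ECG result, whose two abnormal categories are, in Table 35, "Abnormal without clinical significance Abnormal with clinical significance"
- whether a cardiologist was consulted
- below that, "If yes, cardiologist confirm QTcF interval >480msec, n" (%), repeated in the extension table as "interval >480msec, n" (%)
- whether the patient was discontinued after the cardiological examination

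SAP 5.5.3.3 adds that ECG abnormalities will be identified and listed.

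Protocol 7.5.2.2 starts its cardiology procedure "If, at any visit, a QTcF > 480 msec is seen in patients receiving pasireotide LAR". It leaves follow-up to the investigator for an abnormal Visit 10 ECG when no further dose is given. On repeat and extra ECGs, Protocol 7.5.8 says: "Any abnormalities must be recorded in the unscheduled evaluation pages of the eCRF".

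**The concern.** The measure named in 5.5.3 is a number of patients, whereas the tables that should supply it give a number at each visit. The same patient can be flagged at several visits, so the two differ by an unknown amount. Without a definition, two analysts could produce different totals from the same data and both claim to have followed the plan.

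The QT interval is a safety topic that the protocol itself singles out. It excludes patients with QTcF above 450 msec at screening or baseline, and it sets a cardiology procedure at 480 msec. A reader of the report will want to know how many patients crossed the action limit on treatment. The tables as drafted would not say, and the one row that mentions 480 msec could undercount.

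**Working it through.** The plan states no figure for this measure, so there is nothing to reproduce. The check has three parts.

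**1. Does any row give patients ever affected?**

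- QTcF statistics: per visit. The maximum shows whether any scheduled reading exceeded 480 msec at that visit, but not how many patients did, or whether it was the same patient as at another visit.
- Overall result, including clinically significant abnormality: per visit. It does not depend on a consultation.
- Cardiologist-confirmed QTcF above 480 msec: per visit, and only among those with a consultation.
- Overall or any-visit column: absent from both tables.

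The SAP summarises at patient or phase level elsewhere. Table 15 counts patients with at least one adverse event, section 5.5.3.2 compares the baseline laboratory grade with the worst grade on study, and Table 6 has a core-phase column. The ECG tables have no counterpart.

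**2. What do per-visit counts imply about patients?**

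Suppose k patients are flagged at each of V visits among n patients. The number of different patients N then satisfies k ≤ N ≤ min(n, k × V). Inputs are n = 23 (planned enrolment, SAP section 3), V = 8 post-baseline core visits (V3 to V10, Table 35) and V = 6 extension visits (Table B 27). The values of k are assumptions.

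- Core, k = 1: N from 1 to 1 × 8 = 8, which is 1/23 = 4.3% to 8/23 = 34.8%.
- Core, k = 2: N from 2 to 2 × 8 = 16, which is 2/23 = 8.7% to 16/23 = 69.6%.
- Extension, k = 1: N from 1 to 1 × 6 = 6, which is 1/23 = 4.3% to 6/23 = 26.1%. Here 23 is an upper bound on the number of extension patients.

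**3. Which readings above 480 msec can miss the only row that counts them?**

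- A recorded value with no consultation entered. Protocol 7.5.2.2 normally requires the consultation, so this would usually be a deviation, but the value was still observed.
- A Visit 10 value in a patient who receives no further dose, because follow-up is then discretionary. This can happen without any deviation.
- A value from an unscheduled ECG, because neither table has a column for it.

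**The case against.** The strongest reply is that the information is largely there. The row for clinically significant abnormality needs no consultation and is close to the protocol's wording of the measure. The per-visit QTcF maximum makes an extreme scheduled reading visible. The listing in 5.5.3.3 is not limited to scheduled visits, and with 23 patients it can be counted by hand. Under Protocol 7.5.1 a clinically significant abnormal test result becomes an adverse event, and Tables 16 and B 10 report adverse event incidence per patient. Tables 1 and B 1 count patients whose treatment ended because of clinically significant abnormal test results. The consultation condition follows the protocol's own procedure.

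All of this is correct, and it rules out several stronger readings that a reader might infer:

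- **That the data for the measure are lost.** They are not. What is missing is a specified patient-level summary.
- **That notable means QTcF above 480 msec.** Neither document says so. The absence of any definition is part of the problem.
- **That single outliers would be hidden.** The maximum row would show them at scheduled visits.
- **That every unscheduled ECG must be recorded.** Protocol 7.5.8 leaves extra ECGs to the investigator's discretion and asks for abnormalities to be recorded.
- **That the 17.5 msec QTcF effect in the protocol's background applies directly here.** It came from subcutaneous dosing at the maximum tolerated dose in healthy volunteers, not from the LAR formulation.
- **That a count above 450 msec is owed.** That figure is an entry limit only.

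The reply does not supply the count itself. The clinically significant row has the same visit-by-visit limit, a listing is not a specified analysis and cannot be counted consistently without a definition, and adverse events are recorded by sign, symptom or diagnosis rather than by a QTcF limit.

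**Conclusion.** The point holds in a limited form. SAP 5.5.3 promises a patient count for an undefined term, and neither Table 35 nor Table B 27 gives a patient count over visits. The only count above 480 msec can fall short of the readings recorded.

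The size depends on data not yet seen. Under the assumed pattern of one flagged patient at each post-baseline core visit, the table cannot separate 4.3% from 34.8% of 23 patients. That range shows what the layout fails to determine and is not a forecast. If no scheduled QTcF maximum exceeds 480 msec, the scheduled count above that limit is known to be zero, and the question remains only for unscheduled ECGs and for other clinically significant abnormalities. The study is small, single-arm and descriptive, so this is a worthwhile, inexpensive improvement to the safety report and leaves the primary result untouched.

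**What to change.** Add a patient-level block to Tables 35 and B 27, for the safety set and over all post-baseline ECGs, scheduled and unscheduled:

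- n (%) of patients with at least one recorded QTcF above 480 msec, the protocol's own action limit, whether or not a cardiologist was consulted
- n (%) of patients with a cardiologist-confirmed QTcF above 480 msec
- n (%) of patients with at least one clinically significant abnormal ECG

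State in SAP 5.5.3 that these three counts are the clinically notable ECG measure. Keep the per-visit rows. Each patient's maximum QTcF and maximum increase from baseline would be a useful optional addition, but the SAP does not promise it.

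The cost is a few table rows from data already collected, with no change to any clinical procedure. The reported incidence may look less favourable than the per-visit figures.

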	The primary efficacy variable is the proportion of patients with NFPA reaching tumor response, defined as tumor volume decrease of at least 20% after 24 weeks of treatment with pasireotide LAR. The response rate will be summarized in terms of incidence rates and the 90% confidence interval at the end of the Main period of the study (Week 24). The same analysis will be repeated for the PPS population.  Secondary Objectives: All secondary efficacy analyses will be based in the full analysis set (FAS). The safety analysis set will be used for all safety analyses. The secondary efficacy endpoints are described in section 3.3.2.  Safety:
	The safety evaluation will be based mainly on the frequency of adverse events (AEs) and on the number of patients with laboratory values outside the reference ranges. Other safety data, such as physical examination, weight, height, vital signs, ECOG performance status, radiology tests, ECGs, MRIs, and visual evaluations, will be summarized as appropriate.

 	,				
	Calculation of the Sample Size:  The sample size of 19 patients has been selected regardless of statistical power. A response rate (tumor volume decrease ≥ 20%) of at least 10% of patients is considered clinically significant for this population. If the actual response rate is 10%, the probability of obtaining two or more responders among the 16 patients is 58%. In this study, the exact 90% CI will also be obtained. The table below shows the exact 90% CI when 2 - 6 patients, among the 19 patients, respond. Considering a drop-out rate of 20%, 23 patients will be enrolled in order to obtain 19 evaluable patients for the final analysis.				
	Responders / n	Responders / n Lower confidence limi			
	2/19	2/19 1.9% 3/19 4.4%		29.6%	
	3/19			35.9%	
	4/19	7.5%		41.9%	
	5/19	11%		47.6%	
	6/19	14.7%	)	53%	
Planned Dates	FPFV: August 2011	LF	PFV: April 2	2012	
Number of patients, sites, and location of the	Total number of patients: Number of sites: 13	23			

Location of the sites: Brazil

sites

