## 10.5.3.3 Other safety data

Weight, height, and vital signs will be summarized in each period, using descriptive statistics (N, mean, standard deviation, median, minimum, and maximum).

Physical examination abnormalities, ECOG performance status, radiology tests, ECGs, MRIs, and visual evaluations will be identified and listed.

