5.5.3.1 Adverse events

All AEs recorded during the study will be summarized. The incidence of treatment-emergent AEs (new or worsening from baseline) will be summarized by system organ class, severity (based on CTCAE grades), type of AE, relation to the study drug. Deaths reportable as SAEs and non-fatal serious adverse events will be listed by patient and tabulated by type of AE.

Treatment-emergent adverse events (TEAEs) will include all adverse events who started between first and 28 days after the last administration of study medication.

5.5.3.2 Laboratory abnormalities

All laboratory values will be converted into SI units and the severity grade calculated using appropriate Common Toxicity Criteria (CTC).

Frequency of laboratory abnormalities will be displayed by parameter and study day. Notably abnormal laboratory values (new or worsening from baseline based on CTC grades) will be summarized by laboratory parameter. Shift tables will be presented comparing baseline laboratory result (CTC grade) with the worst result (expressed in CTC grade) during study. Patient with abnormal laboratory values will be listed and values outside the normal ranges will be flagged. A separate listing of laboratory abnormalities of CTC grade 3 or 4 will also be provided.

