5.5.3.3 Other safety data

Weight, height and vital signs will be summarized at each time point using descriptive statistics (N, mean, standard-deviation, median, minimum, and maximum).

Abnormalities of physical examination, ECOG performance status, radiological examinations, ECG, MRI, and visual evaluations will be identified and listed.

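### QTcF is summarised only as raw values per visit plus a confirmed >480 msec count; a paired change from the pre-dose Visit 2 ECG would be a cheap and useful addition.

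*SAP*

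**What the plan says.** **Text.** Protocol 10.5.3 names three main safety measures, one of which is the "number of patients with clinically significant changes in ECGs". SAP 5.5.3 gives the corresponding measure as "the number of patients with clinically notable ECG data". Neither section says which ECG findings make up the count.

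The more detailed sections ask for less. Protocol 10.5.3.3 says "Physical examination abnormalities, ECOG performance status, radiology tests, ECGs, MRIs, and visual evaluations will be identified and listed", and SAP 5.5.3.3 says "Abnormalities of physical examination, ECOG performance status, radiological examinations, ECG, MRI, and visual evaluations will be identified and listed". The safety paragraph of the protocol synopsis places ECGs among "Other safety data, such as physical examination, weight, height, vital signs, ECOG performance status, radiology tests, ECGs, MRIs, and visual evaluations".

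**Tables.** SAP Table 35 (core phase, V1 to V10) has these rows at each visit:
- "QTcF (msec) N Mean Median Standard Deviation Minimum Maximum"
- "Normal Abnormal without clinical significance Abnormal with clinical significance Total"
- cardiologist consultation, confirmed QTcF above 480 msec, and discontinuation after cardiological examination.

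SAP Table B 27 (extension, V13 to V28) repeats these rows without V1 or V2. Neither table has a change-from-baseline row.

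**Limits.** Exclusion criterion 11 bars a QTcF above 450 msec at screening or at the pre-dose Visit 2 ECG. Protocol 7.5.2.2 starts the cardiology procedure above 480 msec.

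**The concern.** Protocol 1.2 reports that pasireotide prolongs QTcF and expresses that effect as a change from baseline. The planned tables cannot show such a change within a patient. Three things are lost.

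- **Size of rises below the action limit.** A patient who goes from 400 to 460 msec enters no QTcF threshold count. The ECG is counted only if it is read as abnormal.
- **A like-for-like comparison.** Means at successive visits come from whoever still has an ECG. The set of patients shrinks through drop-out, and again at Week 24, when entry to the extension depends on the physician's view of benefit.
- **Any baseline reference in the extension.** Table B 27 must be read against another table whose patients are not the same.

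The stake is how well the report describes a known effect of the drug. No efficacy result depends on it.

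**Working it through.** The plan states no figure on this point, so there is none to reproduce. The check covers what the planned rows can and cannot show.

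**1. Room below the action limit.** Inputs: entry at 450 msec or less (exclusion 11); action above 480 msec (protocol 7.5.2.2). The largest rise that stays out of the >480 msec row is 480 − baseline.

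| Baseline (msec) | Largest rise not counted (msec) |
|---|---|
| 450 (entry limit) | 30 |
| 430 | 50 |
| 410 | 70 |
| 390 | 90 |

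The first row follows from the documents; the lower baselines are examples.

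**2. Number and timing of ECGs.** Post-dose scheduled ECGs: 8 in the core phase (V3 to V10) and 6 in the extension (V13, V16, V19, V22, V25, V28), so 8 + 6 = 14. V3 falls 20 − 0 = 20 days after injection 1, and V6 falls 76 − 56 = 20 days after injection 3. The other 12 fall 28 days after an injection.

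**3. Visit means with changing patients.** Example: 23 patients have an ECG at baseline and 19 later (the enrolled and evaluable numbers in SAP 5.6). Assume the 4 who leave had a QTcF 20 msec above the mean of the other 19, and that nobody's QTcF changes. The baseline mean is then 4 × 20 / 23 = 3.5 msec above the later mean, so subtracting means shows a fall of 3.5 msec. The paired change in the 19 is 0.

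**4. Precision.** Assume a between-patient SD of 15 to 25 msec, a within-patient correlation ρ of 0.5 to 0.8, and n = 19. Approximate 95% half-width:
- paired, 1.96 × SD × √(2(1 − ρ)/n): 4.3 msec (SD 15, ρ 0.8) to 11.2 msec (SD 25, ρ 0.5)
- visit means compared as if independent, 1.96 × SD × √(2/n): 9.5 to 15.9 msec.

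**5. How noisy a maximum-increase count would be.** The documents give no SD or correlation. Assume normal QTcF, SD 20 msec, exchangeable visits, and s = 20√(1 − ρ). With k post-dose ECGs and cut-off c,

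P(max rise > c) = 1 − E[Φ((c − shift + e₀)/s)^k], e₀ ~ N(0, s²).

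The SD of a single change is 20√(2(1 − ρ)) = 12.6, 17.9 and 21.9 msec for ρ = 0.8, 0.6 and 0.4. Expected patients out of 23, for ρ = 0.8 / 0.6 / 0.4, if all continue:

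| Cut-off, ECGs | No drug effect | 10 msec shift at every visit |
|---|---|---|
| >30, k = 1 | 0.2 / 1.1 / 2.0 | 1.3 / 3.0 / 4.2 |
| >30, k = 8 | 1.2 / 4.8 / 7.5 | 5.6 / 10.2 / 12.5 |
| >30, k = 14 | 1.7 / 6.4 / 9.6 | 7.3 / 12.4 / 14.7 |
| >60, k = 14 | 0.0 / 0.1 / 0.7 | 0.0 / 0.6 / 2.1 |

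With no drug effect at all, up to 9.6 of 23 patients would exceed 30 msec at some visit. The >60 msec count is far less affected by noise.

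**6. What the >480 msec row would catch.** Same model, 10 msec shift, assumed mean baseline of 400 to 420 msec truncated at 450: about 98% or more of single-visit rises above 30 msec end at or below 480 msec.

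**The case against.** The strongest reply is that the SAP already does what the protocol asks.

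**Departure from the protocol.** A reader might infer that the SAP dropped the protocol's word for change. The documents do not support this. Protocol 7.5.2.2 is titled as being about QT changes but is triggered by an absolute value, and 7.5.2.1 on blood glucose likewise uses absolute limits. On that usage the SAP wording is a fair restatement. Protocol 10.5.3.3 asks only for a listing, and Table 35 goes beyond it. This objection stands.

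**No count of patients.** A reader might infer that no per-patient ECG count is planned, or that repeated abnormal readings cannot be traced to patients. SAP 5.5.3 does plan a number of patients. The 5.5.3.3 listing should show who had abnormal ECGs, which is workable with 23 patients. Clinically significant abnormal results are also recorded as adverse events (protocol 7.5.1). This stands too. What remains missing is the make-up of the count and any measure of QTcF increase.

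**Shells are not exhaustive.** SAP 5.5.3.2 promises "Shift tables will be presented comparing baseline laboratory result (CTC grade) with the worst result (expressed in CTC grade) during study", and these have no shell either. A missing row alone is therefore weak evidence. But no SAP text plans a QTcF change, and the text carries the point.

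**Partial remedies exist.** Exclusion 11 already calls the pre-dose V2 ECG baseline, and core means can be subtracted. That does not help in Table B 27, and it does not fix the patient set.

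**The 17.5 msec figure.** It is placebo-corrected, from healthy volunteers at the maximum tolerated subcutaneous dose, two hours after dosing. It cannot serve as the expected size here. It shows only that change is the natural scale.

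**The cut-offs are a choice.** The 30 and 60 msec values are not in the documents, and the >30 msec maximum is mostly noise under plausible variability. That is why paired change should be the main addition.

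**Conclusion.** The gap is real and modest. QTcF is summarised as raw per-visit values and an absolute threshold row, with no within-patient change and no baseline column in the extension. Rises of up to 30 msec can never reach the threshold row for an eligible patient, and rises of 50 to 90 msec can also miss it from the example baselines of 430 to 390 msec. These results need only the entry limit and the action limit. The noise, precision and visit-mean figures rest on assumed variability, correlation, drug shift and drop-out pattern; they show direction and rough size only.

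This does not show a breach of the protocol, a wrong figure or a gap in patient protection. Protection rests on the >480 msec procedure, which is unaffected. It is a worthwhile improvement at low cost.

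**What to change.** 1. In Tables 35 and B 27, add the paired QTcF change from the pre-dose V2 ECG (V1 if missing) at each visit, with the number of pairs. Keep V3 and V6 readable separately, since they fall 20 days after an injection.
2. In SAP 5.5.3, define the notable-ECG count. Each patient counts once if any of these occurs, unscheduled ECGs included: a new reading of abnormal with clinical significance; a confirmed QTcF above 480 msec; or a maximum increase above a cut-off that the sponsor fixes in advance (for example 60 msec). Show the components separately.
3. State the limit: the maximum-increase count is descriptive and is inflated by within-patient variability over up to 14 scheduled ECGs in one arm, especially at 30 msec. Read it with the per-visit paired change and the number of ECGs per patient. The values remain locally read, so differences between sites stay.

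The cost is a few lines of SAP text and added rows in two tables. QTcF is already collected at V1, pre-dose V2 and later visits, so no new data are needed.
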